The comparator group of patients with T2D and CKD untreated with finerenone will consist of all encounters during which an individual was recognised as having CKD and was eligible to be prescribed finerenone but was not. All calendar dates with an encounter with a recorded diagnosis of CKD will be considered as potential Time 0s. The selection criteria (Section 9.2.1.2) will be evaluated at every identified potential Time 0, and all Time 0s meeting the selection criteria will be included in the comparator group. Multiple comparator Time 0s per person may be eligible and selected (Figure 2), including dates for individuals who subsequently initiate finerenone (i.e., information on an individual's future prescription or dispensing for finerenone will not be used to define eligibility). Although this is difficult to confirm before conducting the analysis, the general assumption is that patients with CKD and T2D would visit a physician at least once per year. At each interaction, the physician could potentially recognise the patient as having CKD (i.e., record the diagnosis in the electronic health record [EHR]). When combining the above assumption with an estimated maximum study period of 3 years, we anticipate the number of potential Time 0s per individual in the comparator group to generally be less than 5.

T2D = type 2 diabetes.

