#### 9.2.1.2. Selection criteria

Individuals must meet all the following inclusion criteria on or before Time 0 to be included in the cohort:

- Active registration or continuous enrolment for at least 365 days in the data source before Time 0 (days [-365, 0])
- No recorded use of finerenone before Time 0 (days [-all available, 0])
- Aged 18 years or older on Time 0
- Diagnosis of T2D at any time on or before Time 0 (days [-all available, 0])
- Evidence of CKD on or before Time 0 (days [-all available, 0]), identified by meeting any of the following criteria:
  - A diagnosis code indicating CKD stage 1, 2, 3, 4, or stage unspecified
  - Two UACR test results  $\geq$  30 mg/g separated by at least 90 days and no more than 540 days.
  - Two different eGFR test results  $\geq 15 \text{ mL/min}/1.73 \text{ m}^2 \text{ AND}$ < 90 mL/min/1.73 m^2 [17] separated by at least 90 days and no more than 540 days. If a reported eGFR test result is available in the data, it will be used as recorded to determine eligibility (as that was the eGFR value available to the prescribing clinician at the time of Time 0). If an eGFR value is not reported, but there is sufficient information to calculate the eGFR, it will be calculated using the creatinine-based 2021 CKD-EPI equation [18] (Section 9.3.1).

Individuals will be excluded if they meet any of the following exclusion criteria on or before Time 0:

- Type 1 diabetes (T1D) at any time on or before Time 0 (days [all available, 0]), as finerenone is not indicated for use in T1D
- Evidence of end-stage kidney disease (ESKD) at any time on or before Time 0 (days [all available, 0]) —as finerenone is not recommended to be initiated in individuals with ESKD or severely reduced eGFR—identified as any of the following criteria:
  - Two different eGFR test results < 15 mL/min/1.73 m^2 [17] separated by at least 90 days and no more than 540 days
  - Dependence on dialysis (at least 3 sessions over at least 90 days)
  - A diagnosis code indicating kidney failure or CKD stage 5 (International Classification of Diseases, 10th Revision, Clinical Modification [ICD-10-CM] code N18.5)
  - A diagnosis code indicating having a kidney transplant (ICD-10-CM code Z94.0)
- Diagnosis of kidney cancer at any time on or before Time 0 (days [-all available, 0]), as decreased renal function resulting from kidney cancer may differ in treatment response from diabetic CKD.

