  - Atherosclerosis
  - Atrial fibrillation
  - Cerebrovascular disease (stroke or transient ischaemic attack)
  - Congestive heart failure
  - Hypercholesterolaemia
  - Hyperlipidemia
  - Hypertension
  - Peripheral vascular disease
  - Unstable angina
- Other components of the Charlson Comorbidity Index or similar comorbidity score [48,49] (as single entities, not listed elsewhere)
  - Anaemia
  - Chronic obstructive pulmonary disease
  - Congestive heart failure
  - Dementia

- Human immunodeficiency virus
- Liver disease
- Malignancy other than kidney cancer or nonmelanoma skin cancer
- Paralysis
- Other comorbidities
  - Coronavirus disease 2019 (COVID-19) diagnosis
  - Hyperkalaemia (history of hyperkalaemia, more than 90 days before Time 0)
  - Osteoporosis
  - Pneumonia

The following lifestyle cardiovascular factors will be defined, as available in the data:

- Body mass index or evidence of obesity
- Smoking status
- Alcohol abuse

The following healthcare utilisation measures will be identified in the 365 days before and including Time 0 to characterise patients' healthcare access, healthcare-seeking behaviour, and indicators of disease state at the time of index medication initiation:

- Healthcare utilisation
  - Hospital visits and hospital admissions
  - Emergency department visits
  - Long-term care or skilled nursing facility residence
  - Number of eGFR laboratory tests performed
  - Number of serum potassium laboratory tests performed
- Preventive health services
  - Influenza vaccination
  - Pneumococcal vaccination
  - COVID-19 vaccination
  - Bone mineral density test
  - Screening mammogram
  - Other cancer screening
- Frailty indicators [50]
  - Arthritis
  - Bladder dysfunction
  - Dementia
  - Psychiatric illness
  - Weakness
  - Vertigo

The following comedications will be identified in the 183 days before and including Time 0 to characterise individuals' recent treatments and indicators of disease state at the time of index medication initiation:

- Medications for T2D
  - Alpha glucosidase inhibitors
  - Dipeptidyl peptidase-4 inhibitors (DPP-4i)
  - GLP-1 RA
  - Meglitinides
  - Metformin
  - SGLT2i
  - Sulfonamides
  - Sulfonylureas
  - Thiazolidinediones
  - Insulin
- Cardiovascular medications
  - Angiotensin-converting enzyme inhibitors/angiotensin receptor blockers (ACEi/ARBs)
  - Aldosterone receptor blockers
  - Angiotensin receptor-neprilysin inhibitor
  - Anticoagulants

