### 9.7.5. Exploratory outcome analyses

### 9.7.5.1. All-cause mortality

The analysis of all-cause mortality will be estimated in the overall study cohort without any outcome-specific exclusion criteria. Because there are no competing risks for mortality, weighted treatment group–specific Kaplan-Meier survival plots and overall HR will be estimated without accounting for competing risks.

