To optimise internal validity, this study will assess patients who have been or who could have been prescribed finerenone according to the approved label in the US. Some of these eligibility criteria based on the approved label or treatment recommendations are intended to improve comparability of treated and untreated groups (e.g., exclusion of those with recent hyperkalaemia), thus avoiding comparison of treated individuals with untreated individuals whose clinical state makes them unlikely to be treated and more likely to experience negative outcomes. These criteria are primarily intended to impact the untreated comparison group, but they are also likely to exclude a small number of treated individuals. Consequently, this approach may impact the representativeness of the study results. The study results will be representative of patients prescribed finerenone according to the approved label in the US, but results need to be interpreted with care beyond the labelled indication of finerenone in the US.

A secondary objective of this study will assess the effectiveness of initiating finerenone and titrating dosage according to the approved label by estimating the risk of a composite cardiovascular outcome (i.e., first occurrence of fatal or nonfatal AMI or hospitalisation for heart failure) in patients with CKD and T2D initiating finerenone and uptitrating to 20 mg (when recommended) compared with that in patients with CKD and T2D not using finerenone. Patients in the finerenone group will therefore be censored if they do not seem to follow the titration recommendation from the US label. However, in the control group (no

finerenone use), no such censoring will be possible because these patients do not use finerenone.

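### No exclusion or covariate covers hospice or palliative care, so the exploratory all-cause mortality comparison with nonusers is open to residual bias in favour of finerenone.

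*Protocol*

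**What the plan says.** **Entry.** Section 9.2.1.1 takes comparator entries from any care setting: "All calendar dates with an encounter with a recorded diagnosis of CKD will be considered as potential Time 0s". It adds that "all Time 0s meeting the selection criteria will be included in the comparator group", so one person can enter more than once. The protocol expects generally fewer than five entries per person.

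**Exclusions.** Section 9.2.1.2 opens its list with "Individuals will be excluded if they meet any of the following exclusion criteria on or before Time 0". The items are type 1 diabetes, ESKD, kidney cancer, adrenal insufficiency, hepatic impairment, eGFR below 25, recent raised potassium or hyperkalaemia, strong CYP3A4 inhibitors and pregnancy. Hospice, palliative care and limited life expectancy are not among them.

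**Purpose.** Section 9.9 explains that some of the criteria based on the label or treatment recommendations are meant to improve comparability by keeping out "untreated individuals whose clinical state makes them unlikely to be treated and more likely to experience negative outcomes". Recent hyperkalaemia is its example. It continues: "These criteria are primarily intended to impact the untreated comparison group".

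**Covariates.** The nearest items in 9.3.4 are "Long-term care or skilled nursing facility residence", "Malignancy other than kidney cancer or nonmelanoma skin cancer", dementia, weakness and the other frailty indicators, and hospital admissions. Hospice and palliative care are not named.

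**Mortality analysis.** Section 9.7.5.1: "The analysis of all-cause mortality will be estimated in the overall study cohort without any outcome-specific exclusion criteria". The outcome is exploratory (8.3, 9.3.3.3.1).

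**The concern.** A patient receiving end-of-life care is seldom started on a long-term preventive drug and is likely to die within months. If such patients enter the nonuser group with almost no counterpart among initiators, nonuser mortality rises for reasons unrelated to finerenone and the hazard ratio falls below 1 without any drug effect. Repeated entry can add to this, because frequent contacts late in life yield several Time 0s from the same dying patient. The robust variance in 9.7.3 allows for repeated entries in the confidence interval, but does not change who is being compared.

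Selection criteria are fixed in the protocol. Section 9.3.4 leaves covariate definitions and code lists to the SAP, but not eligibility, so this is not a detail deferred to a later document.

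**Working it through.** **1. The text.** Set side by side, the exclusion list (9.2.1.2) and the covariate list (9.3.4) contain no end-of-life item, whereas the aim in 9.9 describes such patients well. Some are removed by other routes: ESKD, eGFR below 25 or raised potassium in the previous 90 days, hepatic failure or cirrhosis, and kidney cancer. Patients dying of other cancers, heart failure, lung disease or dementia can pass.

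**2. What the default weights do.** Section 9.7.2 uses stabilised inverse probability of treatment weights. An untreated record has weight P(untreated) / (1 - PS). At the 10:1 ratio assumed in 9.5, P(untreated) = 10/11.

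- Record with PS near 0: (10/11) / 1 = 0.91.
- Record with PS at the average of 1/11: (10/11) / (10/11) = 1.00.

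So even when the proxies identify a patient as very unlikely to be treated, the record keeps about 91% of the weight of an average one. A weight of 0.91 is not extreme, so truncating extreme weights would not touch it. ATT weights, PS / (1 - PS), would shrink it towards 0, but they are optional and work only as far as the proxies reveal end-of-life status.

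**3. Possible size.** The protocol gives no mortality figure and no share of records in such care, so there is no stated figure to reproduce and every input is an assumption:

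- 12-month mortality in other patients: 5%.
- 12-month mortality in hospice or palliative care: m = 50% to 70%.
- Share of initiators in such care: 0.1%.
- Share of comparator Time 0s in such care: s = 0.5% to 3%.
- No drug effect.

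Initiator risk = 0.001m + 0.999 x 0.05, which is 0.05045 (m = 50%) or 0.05065 (m = 70%).

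Comparator risk = s x m + (1 - s) x 0.05.

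| s | Comparator risk, m = 50% | Ratio | Comparator risk, m = 70% | Ratio |
|---|---|---|---|---|
| 0.5% | 0.05225 | 0.97 | 0.05325 | 0.95 |
| 1% | 0.05450 | 0.93 | 0.05650 | 0.90 |
| 2% | 0.05900 | 0.86 | 0.06300 | 0.80 |
| 3% | 0.06350 | 0.79 | 0.06950 | 0.73 |

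**4. Sensitivity to the inputs.** With mortality of 4-8% in other patients, 70-90% in end-of-life care and no such initiators, the ratio is 0.82-0.93 at s = 1% and 0.70-0.87 at s = 2%. If initiators have one tenth of the comparator share, s = 1% gives 0.84-0.94.

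These are crude 12-month risk ratios, not the weighted hazard ratio the protocol will report. If weighting on the proxies cut an effective share of 1% to 0.5%, the ratio in the table would move from 0.90-0.93 to 0.95-0.97. How much weighting would really remove cannot be derived from the protocol.

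**5. Scale.** The relative risk assumed for the primary outcome in 9.5 is 0.86. That is a different endpoint, but it shows that a crude distortion from a share of 1-2% is of the same order as the effect the study is sized for.

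**The case against.** Four stronger readings are tempting, and the protocol does not support them.

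- **That the plan contradicts itself.** A reader might infer that 9.9 promises to remove everyone too ill to be treated. It says only that some label-based criteria are intended to improve comparability, and it admits that unmeasured confounding may remain. The list falls short of an aim; it does not break a commitment.
- **That every CKD-coded encounter in the last months of life qualifies.** It does not: the renal, potassium and hepatic exclusions remove part of them.
- **That mortality is biased by a known amount.** The ratios above are unweighted and rest on assumed inputs. Malignancy, chemotherapy, dementia, frailty, admissions and nursing-facility residence are all available for weighting and would take out part of the difference.
- **That the primary result is distorted in finerenone's favour.** Death is a competing event in 9.7.3. Extra nonuser deaths could lower the nonuser cumulative incidence of the composite, which would work against finerenone. The direction is unclear.

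The plan also has general safeguards. Section 9.7.2 inspects propensity overlap and names changed eligibility, added covariates, trimming or truncation of extreme weights, and ATT weights as possible responses. Section 9.9 mentions a sensitivity analysis with restrictive inclusion criteria, and negative control outcomes. These matter but do not close the gap. The responses are conditional, and balance checks on measured characteristics cannot show imbalance in an unmeasured one. The restrictive analysis has no stated criteria and does not appear in 9.7.7. The candidate negative controls (asthma, hand laceration) are sought for a link with healthy lifestyle, not end-of-life status. The confounding example in 9.9 has users sicker than nonusers, which is the opposite direction.

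**Conclusion.** The gap is real and bears on one exploratory outcome. With neither an exclusion nor a covariate for hospice or palliative care, the all-cause mortality hazard ratio is open to residual bias in favour of finerenone. The direction rests on two assumptions: that such patients are rarely started on finerenone, and that they die at a much higher rate than others. The size is unknown. On the assumed inputs the crude ratio with no drug effect is 0.90-0.93 at a 1% comparator share and 0.80-0.86 at 2%, before whatever part weighting removes. No directional claim can be made for the primary outcome. The change is worth making because it is cheap and serves the aim stated in 9.9.

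**What to change.** In 9.2.1.2, for both arms, exclude Time 0s with a hospice claim or a palliative-care diagnosis code on Time 0 or in the 365 days before it (days [-365, 0]), as captured in the data source. Report the number removed per arm with the attrition counts in 9.7.1. Section 9.4 does not say how completely hospice claims are captured, so check this before extraction.

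At minimum, name this status as a propensity-score covariate in 9.3.4, and use the exclusion to define the restrictive-inclusion sensitivity analysis mentioned in 9.9, with an entry in 9.7.7.

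Cost: one eligibility line, one code list and one attrition row. A small share of comparator Time 0s and very few initiators would be lost. Results would no longer apply to end-of-life patients, which slightly narrows the aim in 9.2.3 of including all label-eligible individuals. The kidney cancer exclusion is a precedent, since 9.2.1.2 justifies it by comparability of treatment response rather than by the label.

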## 9.10. Other aspects

## 9.10.1. Statistical reporting

No formal statistical hypotheses will be tested in this study. In accordance with the recommendations of the American Statistical Association [63], the International Committee for Medical Journal Editors [64], and expert opinion on the misuse of significance testing [65-68], we will avoid relying on statistical significance to interpret the study results. Instead of a dichotomous interpretation based on P values and significance testing, we will rely on a quantitative interpretation that considers the magnitude, precision, and possible bias in the estimates that we derive and report. We believe that this is a more appropriate approach than one that ascribes to chance any result that does not meet conventional criteria for statistical significance.

### 9.10.2. Missing data

Data may potentially be missing for some key variables. Data missingness may manifest as explicitly missing fields for certain variables (e.g., no recorded value for race, no height or weight records from which to estimate body mass index interpreted as "missing" or "unknown" values for those variables). Alternatively, for variables defined by the presence of a record in the claims/EHR data, the absence of a record would be interpreted as the variable not being present (e.g., the lack of any prescription or dispensing records for a medication would be interpreted as the patient not using the medication).

For explicitly missing variables fields, the level of missingness will be described. If there is minimal missingness, indicators for missingness may be used as variable values. For some variables (e.g., CKD stage), combinations of different data types may be used to define the variable (e.g., laboratory values or diagnoses) so that if a laboratory value is missing, diagnosis records may be used to define the variable. Additional details will be provided in the SAP.

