### 9.2.2. Study timeframe

The cohort entry period (the time period during which all Time 0s will be identified) will begin on 09 July 2021 (the date of FDA approval in the US) and will end at the latest available data in the data source at the time of analysis. Data from before 09 July 2021 will be used—and potentially back to 01 October 2015, as available—to define selection criteria, washout periods, and covariates.

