#### 9.3.4. Covariate definitions

Covariates include risk factors for renal progression [39,40], cardiovascular outcomes [41,42], or hyperkalaemia [43-45]. Variables potentially associated with the use or non-use of finerenone and the outcomes of interest—e.g., concomitant medications, comorbidities—will be identified for all cohort members before or on Time 0 using diagnosis, procedure, or medication information available in the data source. A detailed description of definitions and code lists for all covariates that will be used in the data source will be specified in the SAP. Covariates will be defined using ICD-10-CM diagnosis codes, laboratory records, procedure coding, or medication coding, as appropriate for each variable.

The following demographic characteristics will be evaluated as of Time 0:

- Age
- Sex
- Calendar year of Time 0
- Race and/or ethnicity (as available in the data)
- Socioeconomic status (as available in the data)
- US geographic region
- Insurance plan type

The following clinical characteristics of patients will be defined using the 365 days before and including Time 0, except where specified otherwise:

- Markers of T2D severity (as available in the data source) and components of the Diabetes Severity Complications Index [46,47] not listed elsewhere
  - Duration of T2D (in all available lookback, as available in the data source)
  - Insulin use
  - Haemoglobin A1c (glycated haemoglobin) (HbA1c) (most recent recorded laboratory value in the 183 days before and closest to Time 0, if available)
  - Hyperosmolar hyperglycaemic state
  - Ketoacidosis

- Lower limb amputations (all available lookback, as available in the data source)
- Neuropathy
- Retinopathy
- Markers of kidney dysfunction severity
  - Duration of CKD (all available lookback, as available in the data source)
  - CKD stage, defined based on eGFR, or stage-specific diagnosis codes (using all available lookback) (Section 9.3.1)
  - Albuminuria stage defined based on UACR values (Section 9.3.1)
  - Proteinuria, defined based on diagnosis codes (Section 9.3.1)
  - Nephrotic syndrome, based on diagnosis codes (Section 9.3.1)
  - Glomerulonephritis
  - Renovascular disease
  - Polycystic kidney disease
  - Autoimmune disease
  - Gout/hyperuricaemia
  - Hospitalisation episodes for acute kidney injury

The following comorbidities will be defined using all available lookback before and including Time 0:

- Cardiovascular comorbidities
  - Acute myocardial infarction

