### 9.7.2. Descriptive analyses

To better understand finerenone treatment patterns, the distribution of baseline finerenone dosage will be described in the treatment group by eGFR and serum potassium levels.

Distributions of the covariates will be described by treatment group. For binary and categorical variables, the frequency distributions (e.g., counts, proportions) will be displayed. For continuous variables, means, standard deviations, medians, first quartiles, third quartiles, first percentile, and 99th percentile will be calculated as appropriate. The relative balance of characteristics across treatment groups (finerenone users vs. comparators) will be described with absolute standardised differences [52] to observe differences in the distribution of characteristics by treatment group. These descriptive analyses will be performed in the crude overall study cohort.

To account for potential confounding resulting from differences in the baseline characteristics of the treatment groups, propensity score methods will be used. Propensity scores will be estimated for each treated and untreated Time 0 using logistic regression with prespecified baseline characteristics as independent variables and finerenone initiation as the dependent variable [53]. After estimation of the propensity scores, the coefficients of the logistic model will be evaluated to understand the relationships between observed covariates and finerenone initiation. The distribution of propensity scores will be plotted by treatment group and assessed. If imbalance of the propensity score distributions is observed (suggesting potential non-exchangeability of the treatment groups), additional steps to improve exchangeability will be considered (e.g., re-evaluation of propensity score variables to ensure that instrumental variables are not included [54], alteration of eligibility criteria to more fully align the treatment groups [55]).

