#### 9.9. Limitations of the research methods

This study will use existing healthcare data. As with all studies based in existing healthcare data sources, the data are generated for healthcare delivery rather than research; thus, missing data or misclassification of study variables is possible.

Written prescription or dispensing data may not reflect actual exposure or nonexposure to finerenone. A prescription issued or a prescription dispensed reflects the intent to use a drug, not actual patient use. Dosage, duration of use, and treatment changes will be estimated from the data; however, not all patient behaviours may be accurately recorded in the data, resulting in potential misclassification of finerenone use, discontinuation date, or dosage.

CKD will be defined using laboratory values (where available) and diagnosis coding. This approach may introduce heterogeneity in the evaluation of CKD severity across study participants. Additionally, formulas for estimating eGFR may vary across time, geographies, and racial and/or ethnic groups. This study will use a standard single equation, CKD-EPI 2021, to estimate eGFR where possible. However, in the absence of complete laboratory records, diagnosis coding will be used, which may lack the granularity of laboratory-based measures.

Cohort entry is defined by meeting electronic algorithms for both T2D and CKD using data available in the data source during the study period. Thus, the original dates of CKD and T2D onset may not be known for each individual. Additional measures of T2D and CKD disease severity will be included as covariates, but duration of illness cannot be considered.

Moreover, specific ordering of the onset of CKD and T2D will not be required. Individuals with T2D who develop CKD may have different treatment patterns and characteristics than those with CKD who develop T2D, but both groups will be included in the present study.

Outcomes will be identified using all relevant diagnosis information using validated algorithms, where available; however, misclassification is possible.

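### Comorbidities are read from person-specific lookback with no record taken as absence, but length of observable history is not a listed covariate; if it differs by arm, the weighted HR can be biased unseen

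*Protocol*

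**What the plan says.** Four provisions of the protocol act together.

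- **Window (9.3.4).** "The following comorbidities will be defined using all available lookback before and including Time 0". The list includes acute myocardial infarction, heart failure, atrial fibrillation, stroke and the Charlson-type conditions.
- **Length of that window.** The minimum is set in 9.2.1.2: "Active registration or continuous enrolment for at least 365 days in the data source before Time 0". The maximum follows from 9.2.2, where earlier data may be used "potentially back to 01 October 2015, as available".
- **Absence rule (9.10.2).** For variables defined by a record, "the absence of a record would be interpreted as the variable not being present".
- **Model (9.7.2).** Propensity scores are estimated "using logistic regression with prespecified baseline characteristics as independent variables".

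Length of enrolment or of observable history appears nowhere in the 9.3.4 covariate list. Three listed covariates carry some of that information: calendar year of Time 0, "Duration of T2D (in all available lookback, as available in the data source" and "Duration of CKD (all available lookback, as available in the data source". Section 9.9, however, says that "duration of illness cannot be considered".

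**The concern.** A condition that is present but unrecorded counts as absent, and the longer a person has been observed, the less often this happens. Suppose the arms have the same true disease burden but one has been observed longer. That arm looks sicker on record. Balancing the recorded conditions then leaves more hidden disease among the apparently unaffected patients of the other arm, and the comparison tilts towards the arm with the longer history.

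The safeguards in 9.7.2 do not look for this. They act on standardised differences of measured characteristics, and those can be near zero while the true conditions are unbalanced. The weights are the main control of baseline confounding in every comparative analysis, so any such distortion would carry through to all of them.

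A difference in lookback is plausible. Under 9.2.1.1 finerenone users enter once, at first initiation, while comparators enter at every eligible CKD encounter, including encounters of people who initiate later. For those people the treated Time 0 necessarily has the longer history. Calendar year adjusts for much of that part, but not for differences in when enrolment or linkage began.

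**Working it through.** **The plan's own figures.** Section 9.5 uses RR 0.86, comparator risk 14.4% or 7.2% and a 10:1 ratio. With a two-sided 5% level, 30,000 records at 14.4% give power of 83.2% (pooled two-proportion formula) or 81.2% (Wald on log RR). At 7.2%, 60,000 records give 80.2% or 78.4%. The stated sizes are consistent with their inputs and do not depend on this point.

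**Range of lookback.** The minimum is 1 year. From 01 October 2015 to 09 July 2021 is 5.8 years. To a Time 0 on 01 October 2024 (the planned start of data extraction, used here as an illustration) it is 9.0 years.

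**Mechanism, one comorbidity.** Assumed, not from the protocol: true prevalence 30% in both arms, comorbidity-outcome RR 2 or 3, recording rate 0.5 or 1.0 per year. From 9.5: true RR 0.86 and treated share 1/11. The gap is to be read as what remains after the other covariates.

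- Capture: s = 1 − exp(−rate × years)
- Recorded prevalence: q = 0.30 × s
- Hidden disease among those without a record: h = 0.30 × (1 − s)/(1 − q)
- Recorded share in the weighted population: P = q₁/11 + 10q₀/11
- Weighted relative risk level per arm: r = P × RR_c + (1 − P) × [1 + (RR_c − 1) × h]
- Estimated RR = 0.86 × r₁/r₀

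Example: finerenone 5 years, comparator 3 years, rate 0.5, RR_c = 2.

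- s₁ = 0.918, s₀ = 0.777; q₁ = 0.275, q₀ = 0.233
- h₁ = 0.034, h₀ = 0.087; P = 0.2369
- r₁ = 0.2369 × 2 + 0.7631 × 1.0340 = 1.2628
- r₀ = 0.2369 × 2 + 0.7631 × 1.0873 = 1.3035
- RR = 0.86 × 1.2628/1.3035 = 0.833

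| Residual gap | Finerenone longer | Comparator longer |
|---|---|---|
| none | 0.860 | 0.860 |
| 1 year | 0.843–0.858 | 0.862–0.876 |
| 2 years | 0.816–0.852 | 0.868–0.902 |
| 4 years | 0.762–0.834 | 0.885–0.951 |

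**What the listed durations absorb.** A simulation set the true effect to null with no true confounding. It assumed 8 correlated conditions at 30% prevalence, each multiplying risk by 1.4, a recording probability of 25–60% per year, mean comparator lookback of 3 years, and finerenone users observed 0.5 to 1.5 years longer.

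- Recorded conditions only: RR 0.890–0.982
- Adding observed T2D and CKD durations: 0.972–0.998
- Adding length of lookback instead: 1.002–1.005

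A second simulation with other assumed disease durations gave 0.95–0.99 with the two durations in the model. Adding one fixed-window marker per condition gave 0.96–0.99. Both simulations yield risk ratios, so they only approximate the effect on the HR.

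**What the fix does.** Lookback was spread over 1, 3, 5 and 7 years and skewed oppositely by arm, with true RR 0.86. With equal true prevalence, recorded comorbidity alone gives 0.804–0.838 (finerenone longer) or 0.881–0.914 (comparator longer); adding lookback returns 0.860. With true prevalence 40% against 30%, adding lookback gives 0.865–0.902, so ordinary under-recording remains.

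**Scale.** Section 9.5 expects at least 20,000 initiators. At 10:1, SE(log RR) = √[(1 − p₁)/(20,000p₁) + (1 − p₀)/(200,000p₀)]. This is 0.0196 at p₀ = 14.4% and 0.0287 at 7.2%, so the unweighted 95% CI is about ±4% to ±6%. A shift of a few percent would be of the same order.

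**The case against.** The strongest reply is that no bias has been shown. A reader might infer that the weighting does bias the primary HR. The protocol does not support that: it gives no lookback by arm, and with equal lookback this source contributes nothing. A reader might also take 0.89–0.98 as the likely size, but that range leaves out the T2D and CKD durations, which 9.3.4 lists. The sentence in 9.9 follows a remark that true onset dates may be unknown, and it can be read as not removing the observed durations. Both parts of this reply stand, and the point is worded accordingly.

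Fixed-window covariates give further protection. Comedications over 183 days and utilisation over 365 days do not depend on total history, and many of the drugs mark the same cardiovascular conditions. This also stands: it narrows the residual but need not remove it.

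The protocol also leaves covariate definitions and missing-data details to the SAP. Code lists and functional form do belong there. The window, the absence rule and the covariate list, however, are set in the protocol itself, and the refinement rule in 9.7.2 would not prompt the addition because it responds to measured imbalance.

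Finally, 9.7.7.1 plans a negative control outcome for residual bias, and 9.9 acknowledges misclassification. Neither targets lookback. The candidate outcomes, asthma visits and hand laceration, are chosen for links with lifestyle and care-seeking rather than cardiovascular history.

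**Conclusion.** The point holds as a conditional weakness. The plan makes comorbidity ascertainment depend on length of observed history and does not list that length for adjustment. If it differs by arm given the listed covariates, the weighted HR can shift in favour of the arm with the longer history, and the planned balance checks would not reveal it.

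Existence, direction and size cannot be determined from the protocol. With assumed gaps of 0.5 to 1.5 years favouring finerenone and both durations in the model, a null RR stays at roughly 0.95 to 1.00. A residual 1-year gap with fast recording is negligible (0.856–0.864 against 0.860). Residual gaps of 2 to 4 years with slow recording would matter. All of this rests on assumed gaps, recording rates and comorbidity effects.

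Sections 9.3.4 and 9.9 must also be reconciled, because the two durations are the closest proxies for lookback in the list. The change is worth making before analysis because it is nearly free.

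**What to change.** 1. In 9.3.4, add length of observable history before Time 0 (days of enrolment or registration) as a prespecified covariate. Enter it in a flexible form in every propensity model.
2. Report its distribution by arm, and its standardised difference before and after weighting.
3. In 9.10.2, state that reading no record as absence relies on this adjustment.
4. Reconcile 9.9 with 9.3.4: say that true time since onset is unknown, and whether the observed durations stay in the model.
5. Optionally, repeat the primary HR with one common fixed comorbidity window. This is supportive only: at the assumed recording rates of 25–60% per year, a 365-day window would miss 40–75% of present conditions.

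The adjustment removes only the part due to differential capture; under-recording common to both arms remains and should be named as a limitation. The cost is a few sentences and one variable obtainable from the enrolment data already needed for the 365-day criterion. No new data are needed, and the study size is unaffected.
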